Linear mixed effects modelling was used to establish whether there were differences in the outcomes of interest between the VR and control groups. Patient-level random effects were considered to account for the repeated outcomes measures. Interaction terms of participant exposure and time were included in each model and used to ascertain whether changes in the outcomes of interest from baseline - before each activity for the daily and before exposure to NPI for the weekly outcomes and at specific time points – during and after each activity for the daily and at day six for the weekly outcome measures – were different between the VR and non-VR groups. Baseline demographic characteristics and duration of exposure to each environment for the daily outcomes were considered for adjustment in the full models. Terms were sequentially removed from the full models if their exclusion did not affect model fit. Reduced models were compared to full models using the Akaike Information Criteria (AIC) and those with the lower values were identified as the final models for each outcome. Using the final models, adjusted values of each outcome per group were estimated and presented as mean summaries with standard errors as a measure of dispersion. The 95% confidence interval (CI) of the fixed effects were estimated using the bootstrapping method and graphical plots of residuals and fitted values were used to determine whether normality and constant variance assumptions were met. To explore potential correlations between video and audio fidelity, and cyber sickness between applications in the immersion survey a two-sample t-test was also used. All analyses were conducted using R statistical software. For more details on the statistical analysis plan, please refer to Appendix A.

Interim analyses

An interim analysis was completed in 2021 (n=52) and indicated no substantive difference between arms, and no significant adverse events. The study was continued to achieve the intended sample size.

Methods for additional analyses (e.g., subgroup analyses)

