The primary analysis will compare mean changes in daily pain before each immersion session and pain scores during and after each session in intervention group to mean changes in daily pain before each immersion session and pain scores during and after each session in control group. Difference in pain score before to time points where it is measured during and after each session (during and after) will be the dependent variable. Study participants will be considered as random effects, treatment group and time together with an interaction term of the treatment group and time as fixed effects. The estimated difference in mean change from before to during, and after immersion sessions and the corresponding 95 % confidence interval (CI) between groups will be presented.

Using a similar approach, the mean changes in weekly pain from baseline measured using the McGill Pain Questionnaire for the overall pain score – combining assessing sensory pain (11 items) and affective pain (4 items) as well as a VAS component scored out of 10, and separately for each component – in intervention group to mean changes in weekly pain in control group will be compared.

Secondary outcomes

Mean changes from baseline in weekly health related quality of life scores and sleep quality index measured using the Health Survey Short Form quality of life and Pittsburgh Sleep Quality Index respectively were compared between the intervention and control groups using the approach like that of weekly primary outcomes.

5. Missing data

When analyzing data for all study participants and those with severe pain, complete case analyses will be conducted for both primary and secondary outcomes. If the number of participants excluded due to missing demographic characteristics is >5% comparisons by assignment arm of those included and those excluded will be conducted to determine if there are any differences in drop out by arm.

References

1. Twombly, R. (2004). What's in a name: who is a cancer survivor? *Journal National Cancer Institute* 96: 1414-15.
2. Canadian Cancer Society and the National Cancer Institute of Canada. *Canadian Cancer Statistics 2008* Toronto: Canadian Cancer Society.

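### The protocol's arm-by-time test and Appendix A's change-score model do not fit together: read on that model, the interaction is zero for a steady VR benefit, although Appendix A does name the right estimate

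*Combined protocol and SAP*

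**What the plan says.** The protocol section on statistical methods for primary and secondary outcomes describes linear mixed models and gives the interaction its role: "Interaction terms of participant exposure and time were included in each model and used to ascertain whether changes in the outcomes of interest" differ between arms. The reference point for change is the score "before each activity for the daily and before exposure to NPI for the weekly outcomes". The section does not say whether the response is the raw score or the change. On the random part it says "Patient-level random effects were considered to account for the repeated outcomes measures". On covariates, "Baseline demographic characteristics and duration of exposure to each environment for the daily outcomes were considered for adjustment in the full models", followed directly by "Terms were sequentially removed from the full models if their exclusion did not affect model fit", with AIC choosing the final model. Confidence intervals for fixed effects come from a bootstrap whose resampling unit is not stated. The reader is then sent on: "For more details on the statistical analysis plan, please refer to Appendix A".

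Appendix A, section 4 (Primary outcome), does name the response. It is the difference from the pre-session score to "time points where it is measured during and after each session (during and after) will be the dependent variable". The model terms follow, with arm, time and their interaction fixed: "Study participants will be considered as random effects, treatment group and time together with an interaction term of the treatment group and time". The same paragraph says that the between-arm difference in mean change to during and to after will be presented with a 95% CI. Weekly McGill scores follow a similar approach from baseline, and the SF-12 and PSQI follow the weekly approach.

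**The concern.** An interaction means different things in the two models. With raw scores and the pre-score as a time level, it is the difference between arms in change. Once the pre-score has been subtracted, that level no longer exists, and the interaction only asks whether the arm difference varies between the remaining time points.

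The only coefficient to which the documents give a testing role is the interaction, in the protocol text. The only response variable they name is the change score, in Appendix A. An analyst who joins the two would test a quantity that cannot see a constant benefit, even though such a benefit makes null hypothesis 1 (Objectives) false. Another analyst, working from Appendix A's promised interval, could report a clear effect from the same data. This concerns both primary outcomes and, through the weekly approach, the secondary ones.

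**Working it through.** **Inputs from the documents.** Steady benefit 10 mm (MCID, Primary Outcomes); 50 per arm, two-sided alpha 0.05, effect 0.5 SD (Sample size); 24 daily sessions; weekly scores at baseline and weeks 1 to 4 (Appendix A, section 2). The documents give no SD in mm and no correlations, so those used below are assumptions.

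**The plan's own figure.** The sample of 100 is not in dispute. With f = 0.25, m measures and correlation rho, a between-factor repeated-measures ANOVA has noncentrality N f² m / [1 + (m - 1) rho]. Assuming m = 4 and rho = 0.7, this is 100 × 0.0625 × 4 / 3.1 = 8.06, with power 80%. The plan states neither m nor rho, and the match has no bearing on this point.

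**1. Coefficients, daily pain.** Illustrative means before/during/after: control 50/46/45, VR 50/36/35.
- Raw scores, pre-score as a time level. Interaction at during: (36 - 50) - (46 - 50) = -10. At after: (35 - 50) - (45 - 50) = -10.
- Change scores: control -4/-5, VR -14/-15. Arm difference: -10 at during, -10 at after. Interaction: (-10) - (-10) = 0.
- If the benefit fell from 10 to 5 mm, the change-score interaction would be (-5) - (-10) = +5. It measures fading, not benefit.

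The zero needs no assumed SD. The same holds for weekly changes at weeks 1 to 4 under a constant benefit.

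**2. Rejection rate of the change-score interaction, steady 10 mm.**
- With a valid standard error it rejects at alpha: 4.6% to 5.4% in simulation (50 per arm, 24 days, rating SD 8 mm, response SD 8 to 20 mm).
- With a participant intercept as the only random effect it rejects less. During and after share one pre-score. With equal, independent rating variance s², after minus during has variance 2s², but the model takes 2s² + 2s² = 4s². The effective critical value is 1.96 × √2 = 2.77, a two-sided rate of 0.6%. Simulation gave 0.5% to 0.8%.
- Weekly, steady 0.5 SD: 4% to 5%.

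**3. Power of Appendix A's arm difference, 10 mm, 50 per arm.** Noncentral t with noncentrality (10/SD) × √(50/2), where SD is that of participants' mean change (assumed):

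| SD (mm) | 12 | 15 | 20 | 25 |
|---|---|---|---|---|
| Power | 98.5% | 91% | 70% | 51% |

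With no effect, this contrast rejected in 4.6% to 5.3% of simulated trials with a participant random effect.

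**4. Raw scores instead.** The interactions now have the right target, but the standard error matters. Assume person SD 20, day SD 12, rating SD 8, a participant intercept only and model-based standard errors. At response SD 8, a participant's mean change has true variance 8² + 2 × 64/24 = 69.3. The model uses about 2 × (144 + 64 + 64 × 2/9)/24 = 18.5. The standard error is too small by √(69.3/18.5) = 1.93, and the false-positive rate is about 31%. Simulation gave 8%, 31% and 47% at response SD 4, 8 and 12. A participant-level effect for change gave 4% to 6%, and a bootstrap resampling participants gave 5.1% to 6.6%.

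**5. Baseline covariate, weekly outcomes.** With unit variance and correlation rho, one week's change has variance 2(1 - rho); after baseline adjustment it is 1 - rho². The ratio is (1 + rho)/2. For the mean of weeks 1 to 4 under compound symmetry, the variances are 5(1 - rho)/4 and (1 + 3 rho)/4 - rho². Power at 0.5 SD, 50 per arm, without and with the covariate:

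| rho | One week | Mean of weeks 1-4 |
|---|---|---|
| 0.3 | 55% to 74% | 75% to 98% |
| 0.5 | 70% to 82% | 88% to 98% |
| 0.7 | 89% to 93% | 98% to 99.6% |

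**The case against.** **Appendix A already states the comparison.** It compares mean changes between arms and promises the difference with a 95% CI, and an interval that excludes 0 is in effect a two-sided 5% test. This stands. A reader might infer that the plan names no usable contrast, or that its primary analysis is blind to a steady benefit. The documents do not support either. Appendix A gives the interaction no testing role, and both places aim at the same quantity. What is left is narrower: which coefficients give that difference, and which result is the test.

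**The protocol text is coherent on raw scores.** This also stands. But that text names no response and refers to an appendix that names a different one.

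**Inflated false positives are not established.** A reader might infer from step 4 that the trial's error rate is too high. The plan speaks of patient-level random effects without limiting them to an intercept, and it plans bootstrap intervals. Resampling by participant keeps the rate at about 5% to 7%. The plan does not state the resampling unit, so inflation is possible but not shown.

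**Model reduction may concern covariates only.** The removal sentence directly follows the covariate sentence, so this reading is plausible. Under a steady 10 mm benefit on raw scores, AIC kept the interaction in all 100 simulated trials, so its loss there is not a practical worry. Protecting the design terms is still worth one sentence.

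**Baseline adjustment is a preference.** Leaving it out costs precision, not validity. Modelling raw scores with baseline as a time level does not recover the gain: with complete data, the unconstrained interaction equals the difference in change.

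**Conclusion.** The point holds as a mismatch between two descriptions of one analysis. The interaction that the protocol uses as its test is exactly 0 for a steady benefit in the model that Appendix A specifies, and it then rejects in at most about 5% of trials. The zero is algebra. The 0.6% rate assumes a participant intercept only and equal, independent rating errors; the power figures assume the SDs and correlations shown.

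The harm is conditional on reading the protocol's test from Appendix A's model. In that case a non-significant test could stand beside a reported interval that excludes 0. The documents do not show that this was done, or that a benefit would go unreported. The plan should be corrected, but its estimand is not wrong. The baseline covariate for weekly outcomes is a separate gain in precision.

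**What to change.** - State one response variable in both the protocol section and Appendix A.
- With change scores: fit arm, time and arm-by-time with participant as a random effect. Name the between-arm difference in mean change at during and at after (weekly: over weeks 1 to 4) as the tested contrast, and say how during and after each count towards the primary outcome. Report the interaction only as a check of stability over time.
- With raw scores: test the interactions against the before or baseline level. Either include a participant-level random effect for change or bootstrap by resampling participants.
- In either case, state the bootstrap's resampling unit and keep arm, time and arm-by-time whatever the AIC.
- In the weekly change-score model, add the baseline score of the same questionnaire as a covariate.
- Label all of this post hoc, because the trial ran to December 2022.

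The cost is SAP wording and, where the fitted model differs, a refit on data already collected. No added patients or visits are needed.

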Due to the global COVID-19 pandemic, the study was paused completely between March 2020 to June 2020. The study was paused two more times (November 2020 - July 2021; Dec 2022) due to pandemic conditions. From June 2020, the study restarted with modified protocols to minimize physical contact and ensure safety according to Behavioural Research Ethics Board guidelines. Participants were screened for COVID-19 exposure and symptoms before each contact. Baseline demographic and outcomes data collection was moved from the set-up session to a teleconference interview session to shorten the session. Participants also received online videos for equipment training to review before the study visit. The set-up session was modified to require personal protective equipment and 2-metre distancing between RA and participant, relying on verbal instructions and demonstrations observed at a distance for training. Weekly check-ins also included screening for COVID-19 symptoms and reassessment of consent. At the end of the participant's 4 weeks, equipment was disinfected during collection then stored in a secure room for 4 days before preparation for use by another participant. When we expanded recruitment across Canada in 2022, we modified the set-up protocol to be completely remote. For participants located outside of BC, participants were shipped all study equipment. For VR, participants received a high-end gaming laptop that could run all VR environments at the highest graphical settings instead of a desktop computer. Participants were asked to view a brief tutorial video on how to set up the equipment. Once the participants received the equipment, an RA would conduct the set-up session via teleconference.

Declarations

Acknowledgements

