Appendix A – Detailed Statistical Analysis Plan

1. Objective

Determine the extent to which VR-based applications are advantageous for daily home-based chronic cancer pain management, compared to equivalent applications experienced on two-dimensional (2D) computer screens.

2. Outcomes

This section presents the outcomes investigated to answer the study objective. The analyses are described in section 3.

Primary outcomes

Visual analogue scale pain scores from 0 to 100mm measured before, during and after an immersion for 24 days.

Weekly pain scores measured using the McGill Pain Questionnaire separately for each component sensory pain (11 items), affective pain (4 items), Visual Analogue Scale component scored out of 10 and overall, as a sum for all three components measured at baseline and at week 1, 2, 3 and 4.

Secondary outcomes

Health related quality of life scores measured using physical and mental health components of the short form quality of life questionnaire and the sleep quality index measured using the Pittsburgh Sleep Quality Index all measured at baseline and at week 1, 2, 3 and 4.

3. Population and Subgroup Analyses

Populations

Intention-to-treat (ITT)

All randomized participants will be included in the analysis as allocated to either the intervention or control arm.

Sensitivity analysis

A subgroup analysis of participants with pain scores before an immersion session will be conducted. Analyses for this population will be used to investigate whether conclusions are sensitive to severity of pain before an immersion session.

Subgroup analyses

Four sub-analyses will be conducted for each application. All sub-analyses groups will be conducted for the overall sample and for the sample with severe pain.

4. Data analyses

All outcomes will be presented using descriptive statistics; normally distributed data by the mean and standard deviation (SD) or standard errors (SE) and binary and categorical variables will be presented using counts and percentages. R software version 2.4.3 will be used for all statistical analysis.

The sections below describe analyses that will be conducted in addition to the descriptive statistics.

Primary outcome

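### The weekly SF-MPQ, SF-12 and PSQI comparisons use change from baseline without adjusting for the baseline score, which costs precision but not validity

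*Combined protocol and SAP*

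**What the plan says.** Appendix A, section 4 sets out the daily VAS model first. The dependent variable is the difference from the pre-session score, participants are random effects, and the model has "treatment group and time together with an interaction term of the treatment group and time as fixed effects". The weekly SF-MPQ, which is a listed primary outcome, follows: "Using a similar approach, the mean changes in weekly pain from baseline measured using the McGill Pain Questionnaire" are compared between arms, for the total and for each component. The secondary outcomes are treated alike: "Mean changes from baseline in weekly health related quality of life scores and sleep quality index" are compared by the weekly approach.

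The baseline values exist. Appendix A, section 2 lists the SF-MPQ by component and "overall, as a sum for all three components measured at baseline and at week 1, 2, 3 and 4", and gives the same schedule for SF-12 and PSQI.

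The main text, under Statistical methods for primary and secondary outcomes, names the candidate covariates: "Baseline demographic characteristics and duration of exposure to each environment for the daily outcomes were considered for adjustment in the full models". It then says "Terms were sequentially removed from the full models if their exclusion did not affect model fit", with AIC choosing the final model, and "Using the final models, adjusted values of each outcome per group were estimated". Neither text enters the baseline value of the outcome as a covariate, and neither constrains the arms to share a baseline mean.

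**The concern.** A change score uses the baseline, but it fixes the baseline coefficient at 1. A covariate lets the data estimate that coefficient. Unless the true slope is 1, the change score leaves removable variance in the comparison. The reference in the main text to adjusted values does not help, because the listed adjustments are demographics and session duration and not the starting score.

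At stake is the width of the confidence intervals for one listed primary outcome (SF-MPQ) and all the secondary scales. The planned size is 50 per arm, and the Sample size section says recruitment feasibility was limited. The extra precision would come from data already held.

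**Working it through.** **1. The plan's own figure.** The Sample size section gives 100 participants (50 per arm) for 0.5 SD, 80% power and two-sided alpha 0.05 under RM ANOVA. The between-factors formula is λ = f²·N·m / [1 + (m − 1)ρ], with f = 0.25 and a noncentral F on 1 and N − 2 df. With m = 2 and ρ = 0.5 it gives N = 98 (81.6% power at 100). With m = 4 and ρ = 0.7 it gives N = 100. The figure is therefore reproducible, but only with a number of measurements and a correlation that the plan does not report. It supplies no ρ for the check below.

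**2. Variance of a single-week contrast.** Let ρ be the correlation of baseline with that week, and k the follow-up SD divided by the baseline SD. In units of the baseline variance, per participant:

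- change score: k² + 1 − 2kρ
- baseline-adjusted, with a slope specific to that week: k²(1 − ρ²)
- proportional cut: (1 − kρ)² / (k² + 1 − 2kρ), which is (1 − ρ)/2 when k = 1

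Example at ρ = 0.5, k = 1: the change score has variance 2(1 − 0.5) = 1.00, the adjusted contrast 1 − 0.25 = 0.75, a cut of 25%.

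Both ρ and k are assumptions. The last two rows use the SF-12 reliabilities cited under Secondary Outcomes (MCS 0.73, PCS 0.82). They are not correlations observed in this trial.

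| ρ | k = 0.8 | k = 1 | k = 1.2 |
|---|---|---|---|
| 0.3 | 49.8% | 35.0% | 23.8% |
| 0.5 | 42.9% | 25.0% | 12.9% |
| 0.7 | 37.2% | 15.0% | 3.4% |
| 0.73 | 36.7% | 13.5% | 2.2% |
| 0.82 | 36.1% | 9.0% | 0.1% |

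The confidence interval narrows by 1 − √(1 − cut). At k = 1 that is 19%, 13% and 8% for ρ = 0.3, 0.5 and 0.7, and 7% and 5% for 0.73 and 0.82.

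**3. Does another reading of the model remove the problem?** The main text can be read as modelling raw scores with baseline as one of the time points. Simulated variance of the week-4 contrast (random intercept, 50 per arm, baseline plus four weeks, constant correlation, 2,000 runs) at ρ = 0.3, 0.5 and 0.7:

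- raw scores with baseline rows: 0.0585, 0.0405, 0.0234
- the same plus a baseline main effect: 0.0585, 0.0405, 0.0234
- raw scores with arm means constrained equal at baseline: 0.0381, 0.0302, 0.0201
- change or post-baseline score with a baseline covariate and no baseline rows: 0.0382, 0.0302, 0.0202

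In a separate simulation at ρ = 0.6, the change-score and baseline-row models gave the same estimates to rounding error. The SD was 0.178 for both, against 0.159 for the two adjusted models. The raw-score reading is therefore no better than the change score, and adding a baseline main effect to it changes nothing.

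**4. One slope or week-specific slopes?** If correlation decays by week as a, a², a³, a⁴ (equal SDs), one common slope is about the mean of those four values. The week-1 variance is then 1 + b² − 2ba.

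- a = 0.8: b = (0.8 + 0.64 + 0.512 + 0.4096)/4 = 0.590, so the variance is 0.404. The change score gives 2(1 − 0.8) = 0.400 and a week-specific slope gives 1 − 0.64 = 0.36.
- a = 0.9: b = (0.9 + 0.81 + 0.729 + 0.6561)/4 = 0.774, so the variance is 0.206. The change score gives 0.200 and a week-specific slope gives 0.19.

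A single baseline slope can therefore be slightly worse than the planned analysis at week 1. Week-specific slopes avoid this.

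**The case against.** The strongest reply is that this is a preference for efficiency. The planned comparison is unbiased under randomisation, and neither its interval coverage nor its type I error is in question. That stands, and the point is limited to precision.

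Second, the size rests on quantities the documents do not give. For SF-MPQ, the one primary scale affected, there is no correlation at all. Over the assumptions tabulated, the cut runs from 0.1% to about 50%. That also stands. The SF-12 reliabilities are only a rough guide and point to the smaller end when SDs are equal. The Discussion adds a further unknown: from June 2020, "Baseline demographic and outcomes data collection was moved from the set-up session to a teleconference interview session", while weekly scores were written in a binder. A mode effect could lower ρ by an unknown amount.

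Third, the lead analysis is daily VAS, and the Outcomes section presents SF-MPQ as a way to examine trends. A reader might infer that the daily comparison loses precision too. The documents do not support that. The daily outcome is already a within-session change, pain is described as highly variable from day to day, and the gain may be nil. The VAS before session 1 is also recorded after allocation, equipment set-up and familiarisation, so it should not be a required covariate.

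Fourth, the data have been looked at. The text reports a first exploration of all outcomes and a 2021 interim analysis. This does not remove the point, but an adjusted analysis could no longer replace the planned one.

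The 40 mm analysis is not an answer. It selects sessions by starting pain and does not adjust the main comparison.

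**Conclusion.** The point holds for the weekly SF-MPQ, SF-12 and PSQI, as a loss of precision only. For a single-week contrast with equal SDs and a week-specific slope, the variance cut forgone is (1 − ρ)/2. That is 35%, 25% and 15% at assumed ρ of 0.3, 0.5 and 0.7, and about 9% to 13.5% at the cited SF-12 reliabilities. At those reliabilities it is near zero if the follow-up SD is 1.2 times baseline. The gain cannot be fixed more closely from the documents.

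Two stronger readings should be resisted.

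- **A fixed saving in participants.** A reader might turn the 35% into a saving (100/0.65 = 154 equivalent participants). That depends wholly on an assumed ρ and equal SDs.
- **A trial too small for its weekly outcomes.** A reader might infer this because change-score power for 0.5 SD at 50 per arm is 71% at ρ = 0.5, against 82% adjusted. At ρ = 0.6 the change score already reaches 80%, and at 0.7 it reaches 90%. The plan does not say which correlation it used.

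**What to change.** Add to Appendix A, section 4, for SF-MPQ (total and each component), SF-12 PCS and MCS, and PSQI:

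- Model the scores or changes at weeks 1 to 4, with baseline records not used as outcome rows. Fixed effects are group, week, group-by-week, the baseline value of that outcome, and baseline-by-week. Exempt the two baseline terms from AIC removal.
- Alternatively, if baseline is kept as a repeated outcome, constrain the arm means to be equal at baseline and use a covariance that lets correlation vary by week.
- Before adjusting, confirm that baseline scores were recorded before the participant was exposed to the arm's equipment. Before June 2020 they were collected at the set-up session, and the assistant responsible for equipment set-up also looked up the arm.
- Report the adjusted result beside the planned one, and label it post hoc if it was added after the data were seen.
- Do not require a baseline covariate for daily VAS.

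The cost is four baseline slope parameters per model (one per week), one extra reported analysis and a check of the baseline timing. No new data or participants are needed.

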Only the researchers identified on this ethics approval will have access to the data. All physical documents and files pertaining to this study were identified only by code number and kept in a locked filing cabinet in a locked office in the UBC School of Nursing. Apart from the password protected single key data file, all data stored on electronic media (computers) at UBC's School of Nursing did not include the name or personal details of the individual subject.

Statistical Methods

Statistical methods for primary and secondary outcomes

A first exploration of all outcomes across all participants was undertaken, using an intention to treat analysis (where all participants were included in the statistical analysis and analyzed according to the group they were assigned, regardless of individual changes in protocol). For the primary outcomes of interest, a minimum clinically important difference (MCID) of 10mm on the VAS scale was adopted. The data exploration also found highly varied pain experiences by many participants throughout the trial, with many beginning their daily activity with pain below a 40mm VAS score, or even with no pain on some days. Hence, a further sub-group analysis was undertaken excluding data from participants whose pre-exposure VAS score was less than 40mm on that day, to explore for effects in this sub-group of participants who were experiencing more substantial pain at the time of the NPI exposure.

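### Appendix A provides for excluding randomised participants whose demographic data are missing, which conflicts with its all-randomised ITT set and is not needed for its primary model

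*Combined protocol and SAP*

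**What the plan says.** Five statements bear on who is analysed.

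- **Analysis set.** Appendix A section 3, under ITT: "All randomized participants will be included in the analysis as allocated to either the intervention or control arm". The main text, under Statistical Methods, describes an ITT analysis "where all participants were included in the statistical analysis and analyzed according to the group they were assigned".
- **Missing data.** Appendix A section 5 says that "complete case analyses will be conducted for both primary and secondary outcomes". It continues "If the number of participants excluded due to missing demographic characteristics is >5% comparisons by assignment arm", the comparison being between those included and those excluded, to look for differences in drop-out between arms. No other reason for exclusion is named there.
- **Primary model.** Appendix A section 4 has participant as the random effect and "treatment group and time together with an interaction term of the treatment group and time as fixed effects". No demographic variable is listed.
- **Covariates.** The main text, under Statistical Methods, adds: "Baseline demographic characteristics and duration of exposure to each environment for the daily outcomes were considered for adjustment in the full models". It then says: "Terms were sequentially removed from the full models if their exclusion did not affect model fit", with AIC deciding between full and reduced models.
- **Extent.** The main-text section on non-adherence and missing data justifies complete case analysis by fewer than 5% of participants having missing data. It does not say which variables were missing.

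**The concern.** The set of all randomised participants and a set that leaves out those with a blank demographic item cannot both be the analysis set. Someone may have supplied three VAS scores on each of 24 days and all four post-baseline weekly assessments. Under section 5 that person could still be left out because a baseline item is blank, and would be counted under the heading of drop-out.

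The section 4 model gives no reason for this, since it never uses the blank item. Under the main-text strategy the item is only a candidate, so the participant may be lost over a covariate that the selection then removes.

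At stake are the claim that the analysis is by intention to treat and, to a small extent, precision. The only safeguard is a comparison by arm that starts above 5%, so smaller losses are not examined at all.

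**Working it through.** **1. Is the exclusion needed for the Appendix A model?** The model needs arm, time, a participant identifier and a change score. Each is available when a demographic item is blank, so the exclusion is not needed.

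**2. Is it needed for the main-text models?** Demographics are candidates there, which explains where the exclusion comes from. There are two ways to run the selection:

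- Fix the rows to those complete on every candidate. AIC values are then comparable, but people are lost over terms that may not survive.
- Let the rows grow as terms are removed. People return, but AIC values from different rows are not comparable.

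The plan does not say which was used, or whether the final model was refitted on all available rows.

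**3. How many participants?** Inputs: planned sample size 100 (Sample size section) and fewer than 5% with missing data of any kind (main text). The documents as supplied give no final number randomised, so 100 is an assumption.

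- Largest whole number below 5% of 100: 4.
- Those 4 would carry at most 4 × 24 × 3 = 288 daily VAS scores and 4 × 4 = 16 post-baseline weekly assessments. These are clustered in four people, so the count of scores overstates the information lost.
- By the rule alone, 5 of 100 is not above 5% and would not trigger the comparison by arm.

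**4. Precision.** SE ratio = √(100/96) = 1.021, so the SE is about 2% larger.

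**5. Power.** The plan's figure is 100 participants for 0.5 SD, 80% power and two-sided alpha 0.05 under repeated measures ANOVA. For the between-group test, f = 0.25 and λ = N f² m / [1 + (m − 1)ρ], with 1 and N − 2 degrees of freedom. The number of measures m and correlation ρ are not given and are assumed here.

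- Smallest even N for 80% power: 98 for m = 2, ρ = 0.5; 100 for m = 4, ρ = 0.7; 98 for m = 5, ρ = 0.7. The planned size is therefore reproducible, but only under chosen values. Over m = 2 to 5 and ρ = 0.3 to 0.8 the range is 58 to 116.
- m = 2, ρ = 0.5: λ = 100 × 0.0625 × 2 / 1.5 = 8.33, power 0.8155. With 96 participants λ = 8.00, power 0.7994.
- m = 3, ρ = 0.7: power 0.7903 with 100 and 0.7735 with 96.

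Either way the loss is under 2 percentage points.

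**The case against.** The strongest reply is that Appendix A and the main text should be read together: section 4 gives the core terms, Statistical Methods gives the candidate covariates and points to the appendix for detail, and section 5 describes what happens in the adjusted models. This stands as an explanation of where the exclusion arises. It does not remove the conflict with the ITT definition, and it confirms that the two descriptions of the model need to be reconciled. Holding rows fixed during AIC selection is also ordinary practice, but it is no reason to leave people out of the primary estimate.

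A second reply is that the case may be rare. The demographics named are age, gender and type of cancer. Age and a cancer diagnosis bear on eligibility, and baseline data were collected at the set-up session or, later, by teleconference interview. The main text also says that partial data were used where possible. This stands, and it limits the size of the problem.

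Three stronger readings are tempting and not supported:

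- *That participants with complete pain scores were in fact excluded.* This is a possible consequence of the rule. No section reports that it happened.
- *That the result is biased.* No arm-related missingness is shown. If missingness is unrelated to arm, dropping these people does not unbalance the arms. Neutrality is not guaranteed either: staff knew the allocation, and baseline data were at first collected at set-up by a team that was not blinded.
- *That the trial loses appreciable power.* A two-sample t-test calculation would give a lower starting power, but that is not the test on which the plan was sized. The loss is small under either approach.

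**Conclusion.** The concern holds as an inconsistency in the analysis set. Section 5 provides for an exclusion that contradicts section 3 and that the section 4 model does not require; under the main-text strategy it can cost a participant over a covariate later deleted.

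The numerical effect is small: at most about 4 of 100 participants and an SE increase of about 2%. This assumes that about 100 were randomised and, as a worst case, that everyone with missing data lacked a demographic item. The power figures also rest on assumed values of m and ρ. The case for change is mainly that the ITT claim should be true as stated, with a minor gain in precision.

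**What to change.** 1. **Appendix A section 5.** State that no randomised participant with pain data is excluded because a baseline characteristic is missing.
2. **Appendix A section 4.** Make the model with arm, time, arm by time and participant, fitted to all of these participants, the primary analysis.
3. **Main text, Statistical Methods.** Amend so that covariate-adjusted, AIC-selected models are secondary. Fill in missing baseline covariates without reference to arm or outcome: the overall mean for a continuous variable; the mode, or a missing category where it is not too sparse, for a categorical one. With four or fewer people affected, a separate category will often be too sparse.
4. **Common rows.** Compare all candidate models on one set of rows. This needs its own sentence, because exposure duration is recorded daily after randomisation and a rule for baseline covariates does not cover it.
5. **Reporting.** Give the number of participants affected by arm, whatever the percentage. If results already exist, report how many were left out on this ground and rerun the primary model with them included.

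The cost is a small amount of extra analysis and an edit to the main text as well as the appendix. Filling in a baseline value is simple, but it should not be described as free of bias in all circumstances; keeping it out of the primary model avoids the question there.
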